3.3 Randomization

All enrolled subjects will be randomized according to the total number of warts and will receive either CellFX or Cryosurgery. Randomization will be implemented through the Electronic Data Capture (EDC) system and will be stratified by the total number of eligible warts (2-4 warts or 5-8 warts). The randomization assignment will include the type of treatment and all randomized subjects will be included in the intent-to-treat (ITT) analysis.

3.4 CellFX Procedure

The intended CellFX treatment device is described as the CellFX® System using the skin contacting component referred to as the “tip” ranging in sizes from 1.5 mm x 1.5 mm to 10.0 mm x 10.0 mm in length and width and may range from 1.0 to 3.0 mm in depth depending on the wart location and size. Each tip will be used with pre-determined energy settings displayed on the CellFX Console and are provided in **Table 1**. These energy settings do not exceed the maximum safe ranges of settings previously tested in clinical studies. A local anesthetic will be used to manage potential treatment discomfort during the CellFX treatment. All subjects will be monitored for muscle “twitching” during each CellFX treatment and the subjects will be asked whether they felt any muscle “twitch” during the treatment.

Table 1: Energy Settings per Tip Size

Tip Size (L x W, mm)	Treatment Level mJ/mm ³
1.5 x 1.5	575
2.5 x 2.5	345
5.0 x 5.0	155
7.5 x 7.5	85
10.0 x 10.0	85

3.5 Standard Cryosurgical Procedure

Cryosurgery will be standardized across all investigational sites. Investigators will perform the Cryosurgical procedure using the Brymill Cry-Ac B700 Liquid Nitrogen Sprayer. Laser or curettage post Cryosurgery will be prohibited. Pulse Biosciences will provide a training video on how to perform the Cryosurgical procedure for training non-blinded treating investigators.

3.6 Site Selection

The study will be conducted at up to 10 clinical research sites. The sites will be selected based on the appropriate patient population, board certified dermatologist, and sufficient resources to support this IDE study.

3.7 Number of Subjects

Up to 150 subjects at up to 10 sites will be enrolled.

3.8 Clinical Study Duration

It is anticipated that the enrollment of subjects in this study will take approximately 3-4 months in duration. All subjects who only receive one treatment will return for follow-up visits at 7-days, 30 days, 60-days, and 90-days or up to a total of 5 study visits. For subjects who receive additional CellFX or Cryosurgery retreatments, at the 30-day or 60-day follow up visit, will return for additional follow-up for 90-days post last treatment or up to a total of 6 or 7 study visits. The total study duration will be approximately 9 months.

4.0 STUDY PROCEDURES

4.1 Screening

Recruitment will be conducted via direct communication by the investigator and/or his/her designated staff, advertisement and/or office ads. The Informed Consent discussion and signature process will be conducted by the investigator and/or designated staff. No study-specific assessments will be performed prior to obtaining consent.

A Screen Failure will be defined as a subject who did not meet one or more of the following criteria:

- Did not meet all of the inclusion and/or exclusion criteria

- Did not sign informed consent
- Did not receive a randomization assignment
- Did not undergo the randomized treatment procedure (e.g. CellFX or Cryosurgery)

A screen failure will not be assigned a subject ID and information on this subject will not be entered in the electronic database. Information will be transcribed on the enrollment/screen failure log.

4.2 Subject Selection

4.2.1 Inclusion Criteria

Candidates for this study must meet **ALL** the following criteria:

1. Subject is at least 18 and no older than 80 years of age.
2. Subject has a Fitzpatrick Skin Type I, II, III or IV.
3. Subject gives voluntary, written informed consent to participate in this clinical investigation and from whom consent has been obtained.
4. Subject must comply with study procedures including all follow-up visits.
5. Subject is willing to have warts treated in a single treatment session and understands that their warts may undergo multiple treatment sessions at subsequent visits.
6. Subject must have a minimum of 2 warts and up to 8 warts to be treated.
7. Subject with a clinical diagnosis of common warts located on hands and fingers or other body areas that are not located on the scalp, nose, within the orbital region of the face, plantar, genital or periungual area.
8. For study purposes, the warts must be no greater than 3 mm in height and must not exceed 10 mm x 10 mm at their largest dimension.
9. Each wart must appear alone and discrete and not appear in clusters.
10. Each wart must have been present for at least 4 weeks.
11. Subject consents to have photographs taken of the warts.
12. Subject agrees to refrain from taking an antihistamine including those used for gastric symptoms(e.g., Loratadine, Desloratadine, Cetirizine, Fexofenadine, Levocetirizine, Azelastine, Ranitidine, Cimetidine, Famotidine, and Nizatidine) up to 48 hours before enrollment and each scheduled follow-up visit, to facilitate an adequate wash-out period.
13. Subject agrees to refrain from using all other wart removal products or treatments (e.g. topical medication including over-the-counter medications) during the study period.

4.2.2 Exclusion Criteria

Candidates will be excluded from the study if **ANY** of the following apply:

1. Subject with more than 8 visible warts in total anywhere on the body.
2. Presence of genital or anal warts will exclude subject participation in study, including treatment of warts on other areas.
3. Periungual, subungual, mosaic, plantar, or filiform warts will not be treated in the study. However, presence of these wart types in addition to warts that meet inclusion criteria will not exclude a participant from the study.
4. Subject has an implantable electronic medical device.(i.e., pacemaker, implantable cardioverter defibrillator)
5. Subject has an active infection or history of infection in designated test area within 90 days prior to first treatment.
6. Subject is prone to Koebnerization or has any of the following conditions (e.g., psoriasis, vitiligo, lichen planus, or an autoimmune disorder of the skin)
7. Subject is not willing or able to sign the Informed Consent.

8. Subject is known to be immune compromised.
9. Subject has allergies to Lidocaine or Lidocaine-like products.
10. Subject is a member of a vulnerable population including pregnant women and individuals employed by the Sponsor, clinic site, or entity associated with the conduct of the study.
11. Have any condition or situation which, in the Investigator's opinion, puts the subject at significant risk, could confound the study results, or may interfere significantly with the subject's participation in the study.
12. Use of any other investigational drug, therapy, or device within the past 30 days of enrollment or concurrent participation in another research study.
13. Subject was previously treated with CellFX for warts.

4.3 Process for Obtaining Informed Consent

Prior to undergoing any study-specific tests or procedures, the subject must sign and date the site's current and approved Institutional Review Board (IRB) informed consent form in order to be eligible for study participation. The informed consent must contain all elements required by 21 CFR Part 50 and ISO 14155:2011/AC:2011 and comply with the ethical principles of the Declaration of Helsinki.

4.3.1 Process for Obtaining Informed Consent

The patients will be informed by the Investigator or Investigator's designee that they are free to refuse participation in this research study. If they elect to participate, it will be made clear that they may withdraw from the study at any time without prejudicing further care.

The Investigator or the Investigator's designee will inform patients that their medical records will be subject to review by the sponsor or appropriate regulatory bodies. This information will be used during the analysis of the results of the clinical study, but the patients' identities will be treated as confidential. Patients will be assigned a unique study subject code that will not reveal the patients' identity, and this code will be used on all data and data collection forms during the study period. The Investigator will explain the conditions of the study, giving the patient sufficient time to ask questions and to consider whether to participate. Eligible patients who agree to participate will be asked to sign and date an IRB-approved informed consent. If the patient agrees, an IRB-approved consent form will be provided to the patient for signature and date. One copy shall be returned to the Investigator and filed in the patient's case history; the other copy is for the patient to keep.

4.3.2 Addition of New Information

Pulse Biosciences, Inc. will revise the written informed consent form whenever new information becomes available that may be relevant to the subject's confirmed participation in the study. The revised information will be sent to the Investigator for approval by the IRB. After approval of the IRB, a copy of this information must be provided to the participating subjects, and the informed consent process as described above needs to be repeated. Please follow the central IRB guidelines on the process of re-consenting subjects.

4.4 Schedule of Events and Evaluations

Schedule of events and evaluations required for this study are provided in **Table 2**.

Table 2: Schedule of Events

Study Activity/ Procedure	Visit 1 Enrollment 1 st TX	Visit 2 7-days Post- 1 st TX	Visit 3 30-days Post- 1 st TX	Visit 4 60-days Post- 1 st TX	Visit 5 90-days Post- 1 st TX	Visit 6 120-days Post- 1 st TX	Visit 7 150-days Post- 1 st TX
	Visit Range	±3 days	±10 days	±10 days	±10 days	±10 days	±10 days
	Consent / Wart Eval / Tx 1	Wart Eval	Wart Eval / Tx 2	Wart Eval / Tx 3	Wart Eval / Final Visit Subject Satisfaction	Wart Eval / Final Visit Subject Satisfaction	Wart Eval / Final Visit Subject Satisfaction
Informed Consent	✓						
Demographics, Medical HX, Fitzpatrick Skin Type, Baseline Wart Size	✓						
Photographs of Non-treated Warts	✓				✓	✓	✓
Subject Randomization	✓						
1 st TX (CellFX or Cryosurgery)	✓						
2 nd TX (CellFX or Cryosurgery)			✓ If required				
3 rd TX (CellFX or Cryosurgery)				✓ If required			
Photographs of Pre and Post Treated Warts	✓	✓	✓	✓	✓	✓	✓
Wart Healing Characteristics	✓	✓	✓	✓	✓	✓	✓
Assessment of Numbness in the Treated Area	✓	✓	✓	✓*	✓*		
Wart Clearance/Resolution			✓	✓	✓	✓	✓
Wart Reduction Assessment		✓	✓	✓	✓	✓	✓
Pain Score/ Assessment for muscle twitching: Treated Warts	✓		✓	✓			
6 Point Subject Satisfaction Scale (SSS)					✓	✓	✓
Adverse Event Assessment	✓	✓	✓	✓	✓	✓	✓
Study Exit					✓	✓	✓

*Numbness assessment will be performed at Visit 4 for those subjects who are retreated at the 30 day follow up visit.

*Numbness assessment will be performed at Visit 5 for those subjects who are retreated at the 60 day follow up visit.

4.5 Screening / Enrollment Procedures

The following evaluations are required at the time of the subject screening/baseline visit.

4.5.1 Activities prior to or on same day as study enrollment

- Evaluation for Inclusion/Exclusion criteria.
- Collect Demographic information and medical history including but not limited to age, gender, race, ethnicity, dermatologic conditions, and Fitzpatrick skin type.
- Sign the consent form prior to any study activities.
- Receive a copy of the signed consent form.

4.5.2 Definition of Enrollment

Once the subject has been consented, randomized, and has received a CellFX or Cryosurgery procedure, the subject will be considered enrolled and each enrolled subject will be assigned a unique Study Identification Number.

4.5.3 CellFX / Cryosurgical Procedures

- Up to 8 clinically diagnosed warts that meet study criteria will be selected by the treating investigator prior to assigning warts or taking baseline enrollment photos
- The treating investigator will conduct a numbness assessment on the selected warts that will be treated
- Photographic images will be collected on all non-treated warts
- The site will log onto the Captivate EDC system. The randomization will include the type of treatment (CellFX or Cryosurgery) that the subject will be assigned
- A template may be used to determine which CellFX treatment tip size will be used for each wart – sizes range between 1.5 mm x 1.5 mm and 10.0 mm x 10.0 mm. Each wart will be numerically labeled using the Canfield two dot system
- The blinded site investigator will perform the baseline/enrollment wart(s) assessment (wart healing characteristics)
- Photographic images of each wart will be taken prior to using local anesthesia/numbing
- Local anesthesia/numbing will only be applied to warts treated with CellFX
- Each subject randomized to CellFX will be treated with pre-determined energy settings; each subject randomized to Cryosurgery will be treated as defined in **Section 3.5**
- The subject will be asked to rate his/her pain immediately after each wart treated with the CellFX and Cryosurgical procedure by using a numerical rating score
- The subjects will be asked whether they felt muscle twitching immediately after each lesion treated with CellFX
- Immediately post-procedure, a wart healing characteristics assessment will be performed by the blinded site investigator
- Photographic images of all treated warts will be taken post-treatment
- A light bandage and/or any physician recommended dressing may be applied before the subject leaves the clinic
- Any adverse events will be identified and documented with a live assessment by the blinded site Investigator

4.6. 7-Day Follow-up Visit

- Photographic images of treated warts will be taken with pre- and post- wart markings
- The blinded site investigator will perform wart(s) assessments (wart healing characteristics and wart reduction)

- Assessment of numbness in the treated area will be performed by the treating investigator
- Any adverse events will be identified and documented with a live assessment by the blinded site investigator

4.7 30-Day Follow-up Visit (CellFX/Cryosurgical Treatment #2, if required)

- Photographic images of all treated warts will be taken with pre- and post-wart markings
- All warts will be clinically assessed by the blinded site investigator (wart healing characteristics, wart clearance and wart reduction assessments)
- Assessment of numbness in the treated area will be performed by the treating investigator

- If any wart is classified as “not resolved”, a second treatment with CellFX or Cryosurgery will be performed to the previously treated wart(s)

In case of a second CellFX or Cryosurgical treatment is required:

- Local anesthesia/numbing will be applied to each wart designated for a CellFX retreatment
- Each wart designated for a CellFX retreatment will be treated using pre-determined energy settings
- Each wart designated for Cryosurgical retreatment will be performed as outlined in protocol **Section 3.5**
- The subject will be asked to rate his/her pain immediately after each wart treated with CellFX and/or Cryosurgery by using a numerical rating score
- The subjects will be asked whether they felt muscle twitching immediately after each lesion treated with CellFX
- Immediately post-procedure, a wart healing characteristics assessment will be performed by the blinded site investigator
- Photographic images of all retreated warts will be taken post-treatment
- A light bandage and/or any physician recommended dressing may be applied before the subject leaves the clinic
- Any adverse events will be identified and documented with a live assessment by the blinded site investigator

4.8 60-Day Follow-up Visit (CellFX/Cryosurgical Treatment #3, if required)

- Photographic images all treated warts will be taken with pre- and post-wart markings
- All warts will be clinically assessed by the blinded site investigator (wart healing characteristics, wart clearances and wart reduction assessments)
- Assessment of numbness in the treated area will be performed by the treating investigator (only for those subjects who received a retreatment at the 30-day follow-up visit)

- If any wart is classified as “not resolved”, a third treatment with CellFX or Cryosurgery will be performed to the previously treated wart(s)

In case of a third CellFX or Cryosurgical treatment is required:

- Local anesthesia/numbing will be applied to each wart designated for a CellFX retreatment
- Each wart designated for a CellFX retreatment will be treated using pre-determined energy settings
- Each wart designated for Cryosurgical retreatment will be performed as outlined in protocol **Section 3.5**
- The subject will be asked to rate his/her pain immediately after each wart treated with CellFX and/or Cryosurgery by using a numerical rating score
- The subjects will be asked whether they felt muscle twitching immediately after each lesion treated with CellFX
- Immediately post-procedure, a wart healing characteristics assessment will be performed by the blinded site investigator
- Photographic images of all retreated warts will be taken post-treatment
- A light bandage and/or any physician recommended dressing may be applied before the subject leaves the clinic
- Any adverse events will be identified and documented with a live assessment by the blinded site investigator

4.9 90-Day Follow-up Visit

- **This is the Final Study visit for any subject for whom all wart(s) were only treated one time**
- Photographic images of all treated warts will be taken with pre and post wart markings
- All treated warts will be classified as “resolved” or “not resolved” by the blinded site investigator
- Wart healing characteristics and wart reduction assessment will be performed by the blinded site investigator
- Assessment of numbness in the treated area will be performed by the treating investigator (only for those subjects who received a retreatment at the 60-day follow-up visit)
- 6-point subject satisfaction scale (for those subjects exiting the study)
- Photographic images will be collected on all non-treated warts (for those subjects exiting the study)
- Any adverse events will be identified and documented with a live assessment by the blinded site investigator

4.10 120-Day Follow-up Visit

- **This is Final Study visit for any subject who have undergone only 2 treatments and/or the last treatment performed at the 30-day follow-up**
- Photographic images of all treated warts will be taken with pre and post wart markings
- All treated warts will be classified as “resolved” or “not resolved” by the blinded site investigator
- Wart healing characteristics and wart reduction assessment will be performed by the blinded site investigator

- 6-point subject satisfaction scale (for those subjects exiting the study)
- Photographic images will be collected on all non-treated warts (for those subjects exiting the study)
- Any adverse events will be identified and documented with a live assessment by the blinded site investigator

4.11 150-Day Follow-up Visit

- **This is Final Study visit for any subject for whom wart(s) were retreated at the 60-day follow-up**
- Photographic images of all treated warts will be taken with pre and post wart markings
- All treated warts will be classified as “resolved” or “not resolved” by the blinded site investigator
- Wart healing characteristics and wart reduction assessment will be performed by the blinded site investigator
- 6-point subject satisfaction scale
- Photographic images will be collected on all non-treated warts
- Any adverse events will be identified and documented with a live assessment by the blinded site investigator

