2.3 Cryosurgical System

The comparator device that will be used in this study is the standard of care procedure using liquid nitrogen to treat warts. The liquid nitrogen procedure uses a single freeze thaw cycle, with warts placed in contact with a metal probe (spray tip) held at liquid nitrogen temperature until a 2 to 3 mm halo is visible around each wart. All physicians are required to use the same Cryosurgical System.

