3.2 Study Design

This study is designed as a prospective, multicenter, single-blinded, randomized comparison IDE study between CellFX System and Cryosurgery. The Principal Investigator will select a sub-investigator to be the blinded investigator to classify the healing characteristics and wart clearance and/or reduction assessment of each subject's selected warts at baseline, post treatment and at 7-days, 30-days, 60-days, and 90-days following the last CellFX treatment or Cryosurgical procedure. This sub investigator will be blinded to the treatment assignment. The subject may not be blinded to the treatment assignment. The Principal Investigator can choose to be the blinded investigator and select a sub investigator to be the treating investigator.

Eligible subjects with a minimum of 2 and up to 8 warts meeting the inclusion and exclusion criteria will be enrolled. If the subject has more than 8 warts, the subject is excluded from the study. Warts may be present anywhere on the face except the scalp, nose and within the orbital region of the face. Plantar warts are also excluded. Subjects will be randomized to receive either a CellFX treatment or Cryosurgery. Selected warts for each treatment modality must be clearly separated in distance from each other so that wart treatment and side effects can be assessed by the blinded site investigator.

All eligible warts will receive at least one CellFX or Cryosurgical treatment. Each subject will be evaluated by the blinded site investigator at 7-days, 30-days, 60-days, and 90-days post-initial CellFX and Cryosurgical treatments. At the 30-day or 60-day follow-up visit, if any wart is classified as “not resolved”, the wart must receive an additional treatment. In case of a second or third retreatment, the subject will be evaluated by the blinded site investigator at 30-days, 60-days, and 90-days post-retreatment. Photography of the warts will be captured along with the blinded site investigator assessments at all visits.

Numbness (diminished/ altered sensation) Assessment: The treating investigator will conduct a “light touch” exam to all treated areas at baseline, 7 days and 30 days post initial treatment and 30 days post retreatment(s). Light touch is tested with a cotton wisp, feather, and/or even light finger touch. The subject will be asked how one area feels compared to another.

Note 1:

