6.1.1 Co-primary Safety Endpoints

The wound healing safety endpoint is the presence or absence of a wound healing safety event at 30 days from the last CellFX or Cryosurgical treatment as assessed by the blinded site investigator. The wound healing safety event is defined as the presence of scabbing, swelling, crusting, blister, scar or ulcer. The timing of the evaluation of this endpoint is wart specific as some warts may not require multiple treatments with CellFX or Cryosurgery. Warts will be categorized as having a primary safety event if any component (scabbing, swelling, crusting, blister, scar or ulcer) is present at the follow-up visit 30 days after the last treatment.

The statistical hypotheses to be evaluated for the wound healing primary safety endpoint are:

$$H_0: p_{CellFX} - p_{Cryo} \geq 15\% \text{ at 30 days post last treatment, versus}$$

$$H_A: p_{CellFX} - p_{Cryo} < 15\% \text{ at 30 days post last treatment}$$

Where p_{CellFX} and p_{Cryo} are the proportion of warts with a composite wound healing safety event (scabbing, swelling, crusting, blister, scar or ulcer) in each treatment group. The null hypothesis will be rejected if the upper bound of the 2-sided 95% confidence interval for the difference in proportions ($p_{CellFX} - p_{Cryo}$) is less than 15%. This approach is equivalent to a 1-sided test with a 2.5% type I error rate.

The skin change safety endpoint is the presence or absence of a skin change safety event at 90 days from the last CellFX or Cryosurgical treatment as assessed by the blinded site investigator. The skin change safety event is defined as the presence of hyperpigmentation, hypopigmentation, or scarring. The timing of the evaluation of this endpoint is wart specific as some warts may not require multiple treatments with CellFX or Cryosurgery. Warts will be

categorized as having a skin change safety event if any component (hyperpigmentation, hypopigmentation, or scarring) is present at the follow-up visit 90 days after the last treatment.

The statistical hypotheses to be evaluated for the skin change primary safety endpoint are:

$H_0: p_{CellFX} - p_{Cryo} \geq 15\%$ at 90 days post last treatment, versus

$H_A: p_{CellFX} - p_{Cryo} < 15\%$ at 90 days post last treatment

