6.1.2 Primary Effectiveness Endpoint

The primary effectiveness endpoint is wart clearance, defined as “resolved” versus “not resolved” at 30 days following the last CellFX or Cryosurgical treatment (30 days post-last treatment) based on the classification of the blinded site investigator. The timing of the evaluation of this endpoint is wart specific as some warts may not require more than 1 treatment with the CellFX System or Cryosurgery. The investigator, blinded to treatment assignment, will classify each wart as “resolved” or “not resolved”.

The primary effectiveness analysis will be a comparison between CellFX and Cryosurgical treatment groups based on 30-day post treatment clearance rate, defined as the proportion of warts classified as “resolved”. This binary outcome classifies warts as completely clear versus not completely clear. The 30-day time-point was selected to reduce the impact of spontaneous wart resolution unrelated to treatment.

The statistical hypotheses to be evaluated for the primary efficacy endpoint are:

$H_0: p_{CellFX} - p_{Cryo} \leq -15\%$ at 30 days post last treatment, versus

$H_A: p_{CellFX} - p_{Cryo} > -15\%$ at 30 days post last treatment

Where p_{CellFX} and p_{Cryo} are the proportion of warts classified as “resolved” in each treatment group. The null hypothesis will be rejected if the lower bound of the 2-sided 95% confidence interval for the difference in proportions ($p_{CellFX} - p_{Cryo}$) is greater than -15%, which is equivalent to a 1-sided test with a 2.5% type I error rate.

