The mean difference in reduction from baseline in wart size of treated warts at 30 days post last treatment will be calculated using a mixed model for repeated measures, with treatment, number of warts stratification and baseline size included as fixed effects. An exchangeable correlation matrix will be used to adjust for within-subject correlation. Least-square mean change, difference, and 95% confidence intervals will be calculated from this model.

6. Wart Resolution Over Time

The rate of wart resolution of the treated warts over time and up to 90 days post last treatment will be calculated.

7. Lesion Observations

Lesion observations at 7-days, 30-days, 60-days, and 90-days post last treatment between CellFX and Cryosurgery. Lesion evaluation includes the following:

- Blister Formation
- Bruising
- Crusting
- Erythema
- Hyperpigmentation
- Hypopigmentation
- Scabbing
- Scarring
- Swelling or Edema
- Ulceration

The rate of each event individually and a composite of any of these events will be calculated for each treatment using the GEE model described in the statistical analysis plan, along with the 95% confidence interval as described for the primary safety endpoint.

8. Satisfaction with Treatment

A 6-point Treatment Satisfaction Scale will be used to measure subject's satisfaction with the treatment of each wart.

[figure not shown]
Table 3: Treatment Satisfaction Scale

Rating	Description
6	Very Satisfied
5	Satisfied
4	Somewhat Satisfied
3	Somewhat Dissatisfied
2	Dissatisfied
1	Very Dissatisfied

The proportion with each response will be summarized. An analysis will be performed using the binary endpoints of satisfied ("Very Satisfied" or "Satisfied") versus not satisfied ("Somewhat Satisfied", "Somewhat Dissatisfied", "Dissatisfied", "Very Dissatisfied") to compare satisfaction across treatment groups. As with treatment-level clearance, the counts and proportions of warts categorized as satisfied will be reported. A GEE model to estimate the treatment difference in the proportion of warts with satisfactory treatment will be performed using the methods described in the statistical analysis plan.

9. Acute Pain Assessment

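### The blinded rater of all three co-primary endpoints also examines the warts right after each procedure, when the arm may be recognisable; reassigning that look removes an avoidable threat to the blind.

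*Combined protocol and SAP*

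**What the plan says.** Section 3.2 calls the study single-blinded and requires a site investigator who does not know the assignment. That person classifies healing and clearance "at baseline, post treatment and at 7-days, 30-days, 60-days, and 90-days following the last CellFX treatment" or cryosurgery. About subjects, the same section says: "The subject may not be blinded to the treatment assignment".

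The blinded investigator is the rater for every co-primary endpoint. In section 6.1.1 both safety composites (wound healing at 30 days and skin change at 90 days after last treatment) are scored "as assessed by the blinded site investigator". In section 6.1.2 clearance at 30 days after last treatment is "based on the classification of the blinded site investigator".

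Section 4.5.3 then schedules a look on the treatment day: "Immediately post-procedure, a wart healing characteristics assessment will be performed by the blinded site investigator". Sections 4.7 and 4.8 repeat it for second and third treatments. The same person makes a live adverse event assessment at those visits (4.5.3, 4.7, 4.8, 10.3.1).

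The plan also describes features that differ by arm:
- Section 2.3: freezing continues "until a 2 to 3 mm halo is visible around each wart".
- Section 4.5.3: "Local anesthesia/numbing will only be applied to warts treated with CellFX".
- Section 3.4: CellFX is delivered through contact tips of equal length and width.

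**The concern.** The blind is asked to hold through the moment at which the arms are most likely to look different. In 4.5.3 the dressing is listed after the assessment, and no masking step or check of the blind is described.

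Randomization is by subject (3.2, 3.3). An assessor who recognises the arm on one wart therefore knows it for all of that subject's warts and carries that knowledge into every later rating. The same assessor's call that a wart is not resolved triggers mandatory retreatment, so knowledge of the arm could also affect the number of treatments and the date from which the 30- and 90-day endpoints are counted.

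There is little independent backup. The three-reader panel (6.2 item 1, 9.0) sees only baseline and 30-day post-last-treatment photographs, judges only resolution, and feeds a secondary endpoint that is not formally tested (6.1.4). Neither safety co-primary has a second blinded reading. If knowing the arm moves ratings toward CellFX, a false finding of non-inferiority becomes more likely.

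**Working it through.** **Is the look needed?** The co-primaries use 30- and 90-day ratings. The lesion endpoint in 6.2 item 7 is defined as "Lesion observations at 7-days, 30-days, 60-days, and 90-days post last treatment between CellFX and Cryosurgery", so it begins at day 7. No listed primary or secondary lesion endpoint uses the immediate score.

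**Could someone else do it?** The treating investigator is present, already does the numbness examination (3.2, 4.5.3), and already follows adverse events to judge relationship (10.0).

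**What could rating bias do?** The documents give no bias size, so the shift *b* below is an assumption.

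Inputs from 6.1 and 6.3: margin 15 points; one-sided 2.5%; 63 subjects per arm with 3 warts each (189 warts); cryosurgery rates 70% (clearance), 43% (wound healing), 40% (skin change); CellFX 75.5%, 37.6%, 32.5%; within-subject correlation ρ = 0.3 for clearance and 0.55 for both safety endpoints.

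Check of the set-up against the plan's figure: for skin change, 90 independent warts per arm give 88% power; the design effect is 1 + 2 × 0.55 = 2.1; 90 × 2.1 = 189 warts, or 63 subjects. This matches 6.3.

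Standard error: SE = √[(p₁q₁ + p₂q₂)(1 + 2ρ) / (3 × 63)]. With the true difference at the margin:
- Clearance, 55% v 70%: SE = 0.0622
- Wound healing, 58% v 43%: SE = 0.0737
- Skin change, 55% v 40%: SE = 0.0736

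One-sided error with shift *b* toward CellFX: 1 − Φ(1.96 − b/SE). For clearance with b = 0.03: 0.03/0.0622 = 0.48, and 1 − Φ(1.48) = 7.0%.

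Trial-wide false success requires all three endpoints to pass. Take clearance at its margin, the safety endpoints at their planned rates, and endpoints independent. Safety power at planned rates is Φ(0.204/0.0730 − 1.96) = 0.798 for wound healing and Φ(0.225/0.0714 − 1.96) = 0.883 for skin change. With no bias, 0.025 × 0.798 × 0.883 = 1.8%. Where all three are shifted, *b* is added to 0.204 and 0.225.

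| Net shift toward CellFX (points) | Clearance error | Each safety error | Trial-wide, clearance only shifted | Trial-wide, all three shifted |
|---|---|---|---|---|
| −5 | 0.3% | 0.4% | 0.2% | 0.1% |
| −3 | 0.7% | 0.9% | 0.5% | 0.4% |
| 0 | 2.5% | 2.5% | 1.8% | 1.8% |
| 1 | 3.6% | 3.4% | 2.5% | 2.7% |
| 2 | 5.1% | 4.6% | 3.6% | 4.1% |
| 3 | 7.0% | 6.0% | 4.9% | 5.9% |
| 5 | 12.4% | 10.0% | 8.7% | 11.2% |

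Independence is a simplification, since one person rates the same warts and scarring sits in both safety composites. Whatever the dependence, trial-wide false success in this scenario cannot exceed the clearance column.

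**The case against.** **Recognisability is inferred.** No section says how a wart looks right after either procedure, whether the halo is still there when the assessor arrives, or whether anesthesia or the tip leaves a mark. This stands, and it is why the claim is only that the arm may be recognisable.

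**The shift is not attributable to this look.** Subjects may know and disclose their arm, and the same assessor sees healing at day 7. The immediate look contributes only what it adds to those routes, which could be nothing. This also stands: the table shows total rating bias. A 1-point shift leaves trial-wide false success near 2.5%, and bias against CellFX would cost power instead. But other possible leaks are no reason to schedule one that serves no listed lesion endpoint.

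**The remedy gives up something.** Section 10.3.1 deliberately wants adverse events assessed blind, and procedure-day events would become unblinded. That is a real cost, but a small one beside the ratings behind all three co-primaries.

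**A masked reading of the safety photographs would cover more routes.** True, and photographs are taken at every visit. It would need extra reader work, and it does not conflict with the simpler change.

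**The baseline step has a similar loose end.** In 4.5.3 the randomization and tip-template steps are listed before the blinded baseline assessment. This is a fair point that the same edit can settle.

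**Conclusion.** The concern holds as a design weakness that should be fixed. The text establishes that the investigator who must stay blind, and who rates all three co-primaries, is scheduled to examine the warts right after every treatment, without masking and without any listed lesion endpoint needing that look.

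That the arm can be recognised then is plausible from the plan's own description but is not shown by it; confidence is medium. The effect on error rates cannot be estimated from the documents. If knowing the arm produced a net shift of 3 to 5 points toward CellFX, per-endpoint error at the margin would be 6.0-12.4% instead of 2.5%, and trial-wide false success 4.9-11.2% instead of 1.8%. These figures assume 63 subjects per arm, 3 warts each, the planned correlations and, for the trial-wide figures, independent endpoints with safety at its planned rates.

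**What to change.** - **Sections 3.2, 4.5.3, 4.7, 4.8:** assign the immediate post-procedure healing assessment, and the record of adverse events arising after treatment that day, to the treating investigator. Remove the post-treatment look from the blinded investigator's duties.
- **Sections 10.0 and 10.3.1:** state that the blinded investigator's live adverse event assessment is done before any treatment at that visit, and that the treating investigator records and reports events arising afterwards that day. Reporting timelines stay as they are.
- **Sequence:** the blinded investigator does the baseline assessment before treatment (preferably before randomization and tip selection), does all follow-up ratings before any retreatment, and does not see treated sites again until the next visit.

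The cost is wording in six sections, with no added staff or visit and no change to treatment rules. The downside is that same-day healing scores and procedure-day adverse events are recorded unblinded. The change closes one route only: subject disclosure and the day-7 appearance remain.
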